10.3.2 Efficacy Analyses

10.3.2.1 Primary Efficacy Analysis

10.3.2.1.1 The Primary Analysis

The primary endpoint (time-normalized number of HAE attacks) will be analyzed using the ITT and PP Populations. The ITT population will be used for the primary analysis and the PP will be used as the secondary analysis.

The evaluation periods for efficacy, including for the time-normalized number of HAE attacks are specified in [Section 10.3](#). For the primary analysis, only the efficacy period for Treatment Period 1 and subjects with q4wk dosing, as defined in [Section 10.3](#), is applicable.

Subjects are to enter HAE symptoms into their eDiary. HAE attacks are based upon review of patient diaries and review of relevant interim medical history by the investigator, including hospital / medical records and any information provided by the subject. Using medical judgment, the investigator is to determine the occurrence of an HAE attack.

The time-normalized number of HAE attacks per month during treatment is calculated per subject as: [the number of HAE attacks / length of subject treatment in days] * 30.4375, where the length of subject treatment is calculated for Treatment Period 1 as: [the date / time of the first SC dose of investigational product in Treatment Period 2 – the date / time of the first SC dose of investigational product in Treatment Period 1].

The time-normalized number of HAE attacks will be summarized descriptively by median (primary) and mean (secondary) with corresponding 95% CIs by treatment (ie, placebo, or [REDACTED] mg, [REDACTED] mg, or [REDACTED] mg CSL312 q4wk).

To test for a difference in the primary efficacy endpoint between [REDACTED] mg CSL312 q4wk or [REDACTED] mg CSL312 q4wk and placebo, pairwise comparisons will be performed by testing the hypotheses using a two-sided Mann-Whitney Test.

To account for multiple testing, the alpha level of 5% will be evenly split between the hypotheses tested. Therefore, the [REDACTED] mg CSL312 q4wk or [REDACTED] mg CSL312 q4wk CSL312 doses (in subjects with C1-INH HAE) will each be evaluated against placebo at $\alpha = 0.025$ for each test:

$$H01: a1 = 0 \text{ vs } H11: a1 \neq 0$$

and

$$H02: a2 = 0 \text{ vs } H12: a2 \neq 0$$

In the above hypotheses, the term “a1” is the shift between the 2 distributions of [REDACTED] mg CSL312 q4wk and placebo and the term “a2” is the shift between the distributions of [REDACTED] mg CSL312 q4wk and placebo, respectively.

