### 4.1.1 Run-in Period

After Screening, eligible subjects will enter the Run-in Period which will last at least 4 and up to 8 weeks. The HAE attacks recorded during Run-in will serve as subject's comparator to the number of attacks which occur under treatment.

Subjects are not permitted to use routine prophylaxis to prevent HAE attacks during the Run-in Period; however, subjects may use on-demand HAE therapy to treat emerging HAE attacks if that medication has previously been shown to be effective.

To enter Treatment Period 1 subjects must have participated in the Run-in period for a minimum of 4 weeks, and among other inclusion and exclusion criteria (see Protocol section 4.1.3) during that time:

- experienced  $\geq 2$  HAE attacks within a consecutive 4-weeks period during Run-in (subjects with C1-INH HAE);
- experienced  $\geq 1$  HAE attack during Run-in (subjects with FXII/PLG HAE).

### 4.1.2 Treatment Period 1

Subjects who are eligible should enter Treatment Period 1 no later than 14 days after Week 9 (Day 57) of the Run-in Period.

Treatment Period 1 will last for around 13 weeks. Subjects may complete the study after Treatment Period 1.

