##### *Treatment Period 1*

In Treatment Period 1, subjects will be randomized using block randomization with fixed block size by means of centralized IRT to 1 of 4 blinded treatment arms:

- The first 32 subjects with C1-INH HAE who are assigned to treatment in Treatment Period 1 will be randomized in a 1:1:1:1 ratio to receive placebo, [REDACTED] mg CSL312, [REDACTED] mg CSL312, or [REDACTED] mg CSL312 q4wk.

For the four blinded treatments above, the 32 C1-INH HAE subjects will be blinded to their treatment assignment. Except for the unblinded pharmacist (or delegate), all investigational site staff including the investigator will also be blinded to the treatment assignment of the 32 subjects with C1-INH HAE in Treatment Period 1. The unblinded personnel will prepare the investigational product but will not administer it to the subjects or assess the subjects. Representatives from CSL (or their delegates) with direct interaction with the study sites or subjects will be blinded to treatment assignment throughout Treatment Period 1. A physical blind ([REDACTED]) will be employed so that blinded study personnel or subjects are unable to detect any difference between CSL312 or placebo. Furthermore, the IV and SC doses will be volume-normalized so that irrespective of the randomized dose, the same volume will be infused or injected to each subject. The assigned IV loading doses will be diluted so that each is the same volume for administration as a dose of [REDACTED] mg (i.e., [REDACTED] mL). The assigned SC doses of CSL312 will be diluted so that each is the same volume for administration as a dose of [REDACTED] mg (i.e., [REDACTED] mL).

In addition, laboratory results which may reveal the treatment allocation will not be available to subjects, study site personnel, or CSL (and delegates) blinded to treatment assignment.

The following laboratory tests may reveal the treatment allocation:

Laboratory Category	Laboratory Test	Comments
Coagulation	CCI	Blinded in eCRF
	CCI	
	CCI	Blinded in eCRF
	CCI	
	CCI	
Immunogenicity	Inhibitory and non-inhibitory antibodies specific to FXIIa antagonist monoclonal antibody	
PK	CSL312 concentration	
CCI	CCI	
	CCI	
	CCI	
	CCI	
	CCI	
	CCI	

Up to 8 additional subjects with C1-INH HAE who are assigned to treatment in Treatment Period 1 after the first 32 subjects (above) will receive CCI mg CSL312 q2wk in an unblinded open-label manner.

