## 4.5 Determination of the Sample Size

### Subjects with C1-INH HAE

Seven subjects assigned to each treatment (placebo, or [REDACTED] mg, or [REDACTED] mg CSL312 q4wk) are needed to reach a power of ~82% for the comparisons of [REDACTED] mg CSL312 q4wk against placebo q4wk and [REDACTED] mg CSL312 q4wk against placebo q4wk in Treatment Period 1.

This is based on the following assumptions:

- Alpha is 2.5% for each of the 2 two-sided Mann-Whitney tests of [REDACTED] mg CSL312 q4wk or [REDACTED] mg CSL312 q4wk against placebo q4wk.
- The time-normalized number of HAE attacks is 2.9 attacks per month during treatment with placebo. This number was derived from CSL study CSL830\_3001, using the lower bound of the distribution-free 95% confidence interval (CI) for the median of the first placebo treatment period.
- The time-normalized number of HAE attacks is 0.6 attacks per month during treatment with [REDACTED] mg or [REDACTED] mg CSL312 q4wk. The number was derived from CSL study CSL830\_3001, using the upper bound of the distribution-free 95% CI for the median of the combined active treatment periods.
- For the time-normalized number of HAE attacks during CSL321 treatment and placebo a Poisson distribution is assumed. The lower bound and the upper bound, respectively, of the CIs for the medians are chosen for the rate parameters.
- Randomization allocation between CSL321 treatment and placebo which are compared are equal.

[REDACTED]

[REDACTED]. The sample size of 7 subjects for this arm is not driven by an

efficacy comparison, but instead, by consistency with other treatment arms and for maintenance of the blinding of the study. No testing for efficacy of the [REDACTED] mg CSL312 dose against placebo is planned and no power calculation has been done.

An additional subject will be added to each of these 4 treatment arms to account for dropouts during Treatment Period 1, resulting in 8 subjects required in each treatment arm.

Up to 7 subjects with C1-INH HAE will be assigned to receive [REDACTED] mg CSL312 q2wk. This arm is included for informational purposes, and therefore no testing against placebo is planned and no power calculation has been done. An additional subject will be added to this arm to account for dropouts during Treatment Period 1, resulting in up to 8 subjects in this treatment arm.

Overall, a total of up to 40 subjects with C1-INH HAE will be assigned to treatment in Treatment Period 1.

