## 10.1 Primary Efficacy: Analysis of Time-Normalized Number of HAE Attacks in Treatment Period 1 (Blinded Part)

The ITT population will be used for the primary analysis and the PP will be used as the secondary.

As outlined in Section 8.2.8, HAE attacks with a start date not falling into the efficacy evaluation period will not be included in the analyses of efficacy but will be presented in a listing only.

Subjects will enter HAE symptoms into their eDiary and the start and end date and time, the interference of HAE symptom(s) with daily activities, and location(s) of the HAE symptom(s). Investigator-reported HAE attacks will be based upon review of subject diaries, relevant interval medical history, and physician judgment. The investigator may ask clarifying questions to assist in his/her assessment of whether or not an HAE attack occurred. If an attack occurred, then the investigator will record an attack in the eCRF, the start/end date, the attack location(s), and the severity of the attack based on the most severe symptoms. For every visit, the Investigator will report all HAE attacks that have occurred in the interim since the last visit the subject attended.

For the analyses, a HAE attack is defined based on the HAE attacks reported by the investigator using the HAE attack eCRF.

In the primary analysis, only subjects with C1-INH HAE who receive q4wk SC dosing (after an IV loading dose) in a blinded manner will be included. The evaluation periods are defined in Section 8.2.8.

The time-normalized number of HAE attacks per month during Treatment Period 1 for a subject will be calculated as:

$$(\text{number of HAE attacks} / \text{length of subject's evaluation period in days}) * 30.4375$$

where the length of subject's evaluation period is defined in Section 8.2.8.

The time-normalized number of HAE attacks per month will be summarized descriptively including median (primary) and mean (secondary) with corresponding 95% CIs by blinded treatment (i.e., placebo, or bci mg, bci mg, or bci mg CSL312 q4wk).

To test for a difference in the primary efficacy endpoint between [b] mg CSL312 q4wk or [b] mg CSL312 q4wk and placebo q4wk, pairwise comparisons will be performed by testing the hypotheses using a two-sided Mann-Whitney test.

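### The confirmatory Mann-Whitney tests leave the Run-in attack rate unused, so a chance baseline imbalance between arms of 8 goes uncorrected; the gain from adjusting depends on variability that the plan does not state

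*SAP*

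**What the plan says.** SAP 10.1 sets the confirmatory test: "pairwise comparisons will be performed by testing the hypotheses using a two-sided Mann-Whitney test". Protocol 10.3.2.1.1 says the same: "pairwise comparisons will be performed by testing the hypotheses using a two-sided Mann-Whitney Test". Neither names a covariate or a stratum. The response is the Treatment Period 1 attack rate per month, and each dose is tested against placebo at a two-sided alpha of 0.025.

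On allocation, SAP 4.4 says that in Treatment Period 1 "subjects will be randomized using block randomization with fixed block size by means of centralized IRT", with no stratification factor. Treatment Period 2 randomisation is stratified, but only by the previous arm.

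Protocol 4.1.3 requires at least 28 days of Run-in before Treatment Period 1 and, for C1-INH HAE, at least 2 attacks within 4 weeks. A Run-in rate therefore exists for every subject in the primary comparison. SAP 4.1.1 gives it a role: "The HAE attacks recorded during Run-in will serve as subject's comparator to the number of attacks which occur under treatment".

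In the readable text that role is met by the responder endpoint (SAP 10.2.1) and by the subject profiles (SAP 10.1.2), which also show the Run-in Period. The baseline summary in SAP 9.3 gives attack counts before Screening, or before prophylaxis began, but not the Run-in rate. The only readable sensitivity analysis of the primary test is the tipping-point analysis for missing values (SAP 10.1.1).

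**The concern.** A subject's own recent attack rate is the obvious candidate predictor of the rate on treatment. With 8 per arm, one or two high-frequency subjects falling in the same arm can shift the ranks, and an unadjusted test cannot separate that from a drug effect. Both dose tests share one placebo arm, so an unlucky placebo arm affects both. The study is meant to guide dose selection for phase 3 (protocol 3.3.1), and only one randomisation will be available to interpret.

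If the Run-in rate predicts well, using it would also sharpen both comparisons at the same alpha with no new data. That matters most if a dose works less well than planned.

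**Working it through.** **Inputs from the plan (SAP 4.5, 8.2.8).** "The time-normalized number of HAE attacks is 2.9 attacks per month during treatment with placebo"; 0.6 per month on either tested dose, a ratio of 0.6/2.9 = 0.21; Poisson counts; two-sided alpha 0.025 per test; 7 per arm plus 1 for dropout = 8; evaluation window Day 6 to Day 91, which is 85 days or 85/30.4375 = 2.79 months.

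**Inputs not in the documents, assumed here.** Between-subject CV of attack rates, Run-in/treatment correlation, drift of a subject's rate between periods, and effects weaker than planned.

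**1. The plan's own figure.** SAP 4.5 says that seven per arm "are needed to reach a power of ~82% for the comparisons of" dose against placebo. A normal approximation with Mann-Whitney efficiency 3/π reproduces this:
- SD = √((2.9 + 0.6)/2) = 1.323; difference = 2.3; effective n = 7 × 3/π = 6.68.
- z = 2.3/(1.323 × √(2/6.68)) − 2.241 = 0.94, so power = 82.6%.

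This model has one Poisson rate per arm, so the Run-in rate carries no information in it.

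**2. Chance imbalance.** In SD units, the difference between two arm means of 8 has standard error √(2/8) = 0.5. A gap of at least 0.75 SD is 1.5 standard errors, which happens in about 13% of randomisations. Null simulations (5,000 trials, outcome Poisson 2.9, assumed correlation on a latent normal scale, nominal 2.5%) gave:

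| Assumed correlation | Mann-Whitney, all trials | Mann-Whitney, gap ≥ 0.75 SD | Run-in-adjusted, gap ≥ 0.75 SD |
|---|---|---|---|
| 0.3 | 1.8% | 3.0% | 1.1% |
| 0.5 | 2.0% | 6.5% | 1.8% |
| 0.7 | 2.0% | 8.5% | 1.8% |

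The conditional Mann-Whitney entries rest on about 650 trials each (13% of 5,000), so their error is about 0.7 to 1.1 points. Overall size is kept; the excess appears only in the imbalanced randomisations.

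**3. Power if subject rates are stable.** Gamma rates with mean 3 per month, the protocol entry rule, Run-in exit at day 28, 42 or 56, 85-day window, 8 per arm, exact permutation tests, 8,000 comparisons per scenario. Entries are Mann-Whitney → rank ANCOVA on the Run-in rate, in per cent:

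| Between-subject CV | Ratio 0.4 | Ratio 0.3 | Ratio 0.21 (planned) |
|---|---|---|---|
| 0.4 | 68 → 70 | 88 → 88 | 97 → 96.5 |
| 0.6 | 52 → 60 | 75 → 81 | 91 → 92 |
| 0.8 | 42 → 54 | 63 → 75 | 84 → 90 |

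At CV 0.6 to 0.8 the gains are 6 to 12 points at ratios 0.3 and 0.4 (about 5 to 12 allowing for simulation error) and 1 to 6 points at the planned ratio. Null rejection was 2.2 to 2.4% unadjusted and 2.4 to 2.7% adjusted.

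**4. Power if the Run-in rate predicts poorly.**
- One common rate per arm, the plan's model: 100 → 99.1% at ratio 0.21, 96.2 → 94.0% at 0.35, 74.5 → 71.8% at 0.5. Adjustment costs up to about 3 points.
- Rates that drift (lognormal period-to-period CV 0.5, error about 1 point). With between-subject CV 0.6: 34.3 → 35.5% at ratio 0.4, 54.1 → 55.9% at 0.3, 76.3 → 76.5% at 0.21. With CV 0.4: 67.4 → 65.6% at 0.3, 84.5 → 82.3% at 0.21.

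**5. Can the plan settle the CV?** Only by inference. If the monthly rate itself is taken to have Poisson variance 2.9, counting noise over 2.79 months explains 2.9/2.79 = 1.04. The remaining 1.86 implies a placebo CV of √1.86/2.9 = 0.47. At that CV, runs of 1,500 trials gave 73 → 77% at ratio 0.35 and 95 → 95% at 0.21. The plan does not state this reading, and the single-rate reading is equally open.

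**The case against.** The strongest reply is that the prespecified test is valid and adequately powered. Randomisation controls its overall error rate. At the planned effect its simulated power in the table above is 97, 91 and 84%, all above the stated 82%. The larger gains need weaker effects than the sponsor assumed. They also need stable subject rates, yet routine prophylaxis stops only on the first day of Run-in (protocol 4.1.1 and 7.3), so Run-in may include washout. All of this stands, and it is why the gain is stated as conditional.

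The reply also notes that baseline attack frequency is not invisible. SAP 9.3 tabulates historical counts, the profiles show Run-in, and the responder analysis normalises to it. That softens the point, but none of these corrects the primary comparison.

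Three stronger readings are tempting and not supported:
- *The trial gives up several points of power.* This needs a variance or a correlation that the documents do not give. Under the plan's single-rate model, adjustment loses power.
- *The primary test is biased or inflates type I error.* It does not do so overall; the excess is conditional on an imbalanced randomisation.
- *The plan contains no Run-in-adjusted analysis.* SAP 10.1.3 to 10.1.5, and parts of SAP 4.6.1, SAP 10.2.1 and protocol 10.3.2.1.2, are redacted. A supportive analysis of this kind may already be there.

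**Conclusion.** The point holds in a limited form. The confirmatory comparison does not use a baseline value that every treated subject has, and with 8 per arm and no stratification it cannot correct a chance imbalance in attack rate. A gap of at least 0.75 SD arises in about 13% of randomisations. In those, the false-positive rate is about 3 to 8.5% for assumed correlations of 0.3 to 0.7, against a nominal 2.5%.

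The effect on power can be material or nil. Which applies turns on between-subject spread, on stability between Run-in and treatment, and on the true effect, and the documents settle none of these. This justifies a supportive analysis and a clearer baseline table. It does not show that the confirmatory test is wrong.

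**What to change.** Keep both Mann-Whitney tests, their alpha and their confirmatory status. Add to SAP 10.1 a prespecified analysis, labelled supportive, for each tested dose against placebo:
- Within the pair of arms, rank the Treatment Period 1 rates and the Run-in rates.
- Regress the first set of ranks on the second and compare the residuals between arms.
- Take an exact permutation p-value over all C(16,8) = 12,870 allocations.

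Add the Run-in attack rate by arm to the SAP 9.3 baseline summary. If a redacted section already holds such an analysis, only the baseline row is needed.

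The cost is one SAP paragraph, a short program and one table row. The downside is one more analysis to interpret, with up to about 3 points less power than the Mann-Whitney test when the Run-in rate predicts poorly.

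Making the adjusted test primary is a larger step. It would change the protocol synopsis and 10.3.2.1.1, and SAP 4.2.1, 4.6.1, 10.1 and the tipping-point analysis in 10.1.1. It should be done only by protocol amendment, before anyone deciding it has seen unblinded data. That includes IDMC outputs: under SAP 4.6.2 these go to unblinded sponsor personnel and include attack-rate tables from the third review, which SAP 4.1 planned for May or June 2019, ahead of SAP version 2.0 of June 2020.
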